8.2.3. Electrocardiogram (ECG)

A standard 12-lead ECG will be conducted at the Week -2 visit. Electrocardiograms will be conducted and read at the investigator site or affiliated facility. Significant findings that are present must be documented in the source and eCRF.

During the collection of ECGs, subjects should be in a quiet setting without distractions (eg, television, cell phones). Subjects should rest in a supine position for at least 5 minutes before ECG collection and should refrain from talking or moving arms or legs. If blood sampling or vital sign measurement is scheduled for the same time point as ECG recording, the procedures should be performed in the following order: ECG(s), vital signs, blood draw.

8.2.4. Clinical Safety Laboratory Assessments

Blood samples for serum chemistry and hematology, and urine samples for urinalysis will be collected. The investigator must review the laboratory results, document this review, and record any clinically relevant changes occurring during the study in the adverse event eCRF if applicable.

Subjects will be monitored for safety laboratory analytes as described in [Appendix 9](#), Clinical Laboratory Tests.

Subjects with elevations in ALT ($\geq 3 \times$ ULN), in lipase/amylase ($\geq 2 \times$ ULN) or in calcitonin (≥ 10 pg/mL [≥ 10 ng/L]) will be monitored and managed using the algorithms provided in [Appendix 10](#), Algorithm for Monitoring Abnormal Liver Function Tests, [Appendix 11](#), Pancreatitis Monitoring and Withdrawal Criteria, and [Appendix 12](#), Guidelines for Calcitonin Monitoring.

In the current study, serum β -hydroxybutyrate will be assessed by the central lab as a marker of target engagement as mild elevations of serum β -hydroxybutyrate were generally observed in the Phase 1 studies (see Section 2.3, Benefit/Risk Assessment). To avoid the potential unblinding of subject to treatment assignment, both serum β -hydroxybutyrate and urinary ketones will remain masked to investigators and sponsor.

Alerts will be provided to investigators by the central laboratory identifying important laboratory changes or key out-of-range values, so the investigator can follow-up as necessary. For creatinine phosphokinase (CPK) elevations, the investigator should determine if follow-up evaluation is clinically appropriate to exclude a potential cardiac event.

8.3. Adverse Events and Serious Adverse Events

Timely, accurate, and complete reporting and analysis of safety information from clinical studies are crucial for the protection of subjects, investigators, and the sponsor, and are mandated by regulatory agencies worldwide. The sponsor has established Standard Operating Procedures in conformity with regulatory requirements worldwide to ensure appropriate reporting of safety information; all clinical studies conducted by the sponsor or its affiliates will be conducted in accordance with those procedures.

Anticipated events will not be recorded and reported in this study as to allow full reporting of AEs from these studies without any special reporting exceptions for individual case safety reports of AEs.

For further details on AEs and SAEs (Definitions and Classifications; Attribution Definitions; Severity Criteria; Special Reporting Situations; Procedures) as well as product quality complaints, refer to [Appendix 1](#), Adverse Events: Definitions and Procedures for Recording, Evaluating, Follow-Up, and Reporting.

Collection of Protocol-Specified Adverse Events of Interest

For any adverse event considered to be one of the following protocol-specified adverse events of interest, and for all deaths, investigators may be asked to provide more detailed information with the source documents or completing the applicable supplemental forms or eCRF.

Cardiovascular Events

Investigators will be instructed to identify the following cardiovascular events of interest:

- MACE (ie, CV death, nonfatal MI, and nonfatal stroke)
- hypotension-related AEs

Pancreatic Events

Investigators will be instructed to identify the following pancreatic events of interest:

- adverse event of pancreatitis
- adverse events of serious or severe abdominal pain leading to suspicion of pancreatitis
- confirmed lipase or amylase elevations $\geq 3 \times$ ULN.

See [Appendix 11](#), Pancreatitis Monitoring and Withdrawal Criteria, for details of how to monitor and document pancreatic adverse events.

Calcitonin Elevation and Thyroid Neoplasm

Investigators will be instructed to identify elevations in calcitonin and possible cases of thyroid hyperplasia, including but not limited to:

- C-cell thyroid hyperplasia
- Medullary thyroid cancer
- Thyroid cancer (papillary, follicular)
- Thyroid nodule
 - See [Appendix 12](#), Guidelines for Calcitonin Monitoring, for details of how to monitor and document thyroid neoplasm.

Collection of Information on Possible Hypoglycemic Episodes

Subjects will be asked to collect fingerstick glucose determinations at the time of possible hypoglycemic episodes, and to document information on these events, including the fingerstick glucose results, in the blood sugar diary. This diary will be reviewed by study-site personnel at each scheduled visit (see [Appendix 8](#), Hypoglycemia: Definitions, Symptoms and Treatment). Information on possible hypoglycemic episodes will be collected on a separate hypoglycemia eCRF, and hypoglycemic episodes that are considered by the investigator to be adverse events of hypoglycemia should also be recorded on the adverse event eCRF.

8.3.1. Time Period and Frequency for Collecting Adverse Event and Serious Adverse Event Information

All Adverse Events

All adverse events and special reporting situations, whether serious or non-serious, will be reported from the time a signed and dated ICF is obtained until completion of the subject's last study-related procedure, which may include contact for follow-up of safety. Serious adverse events, including those spontaneously reported to the investigator within 5 weeks after the last dose of JNJ64565111/placebo after the last dose of study drug, must be reported using the Serious Adverse Event Form. The sponsor will evaluate any safety information that is spontaneously reported by an investigator beyond the time frame specified in the protocol.

Serious Adverse Events

All SAEs occurring during the study must be reported to the appropriate sponsor contact person by study-site personnel within 24 hours of their knowledge of the event.

Information regarding SAEs will be transmitted to the sponsor using the Serious Adverse Event Form and Safety Report Form of the eCRF, which must be completed and reviewed by a physician from the study site, and transmitted to the sponsor within 24 hours. The initial and follow-up reports of an SAE should be transmitted electronically or by facsimile (fax).

8.3.2. Follow-up of Adverse Events and Serious Adverse Events

Adverse events, including pregnancy, will be followed by the investigator as specified in [Appendix 1](#), Adverse Events: Definitions and Procedures for Recording, Evaluating, Follow-up, and Reporting.

8.3.3. Regulatory Reporting Requirements for Serious Adverse Events

The sponsor assumes responsibility for appropriate reporting of adverse events to the regulatory authorities. The sponsor will also report to the investigator (and the head of the investigational institute where required) all suspected unexpected serious adverse reactions (SUSARs). The investigator (or sponsor, where required) must report SUSARs to the appropriate Independent Ethics Committee/Institutional Review Board (IEC/IRB) that approved the protocol unless otherwise required and documented by the IEC/IRB. A SUSAR will be reported to regulatory authorities unblinded. Participating investigators and IEC/IRB will receive a blinded SUSAR summary, unless otherwise specified.

8.3.4. Pregnancy

All initial reports of pregnancy in female subjects or partners of male subjects must be reported to the sponsor by the study-site personnel within 24 hours of their knowledge of the event using the appropriate pregnancy notification form. Abnormal pregnancy outcomes (eg, spontaneous abortion, fetal death, stillbirth, congenital anomalies, or ectopic pregnancy) are considered SAEs and must be reported using the Serious Adverse Event Form. Any subject who becomes pregnant during the study must discontinue further study treatment.

Follow-up information regarding the outcome of the pregnancy and any postnatal sequelae in the infant will be required.

8.4. Treatment of Overdose

For this study, more than 3 doses/injections of JNJ-64565111 within a 7-day time period will be considered an overdose.

In the event of an overdose, the investigator or treating physician should:

- Contact the Medical Monitor immediately.
- Closely monitor the subject for AE/SAE and laboratory abnormalities.

No antidote to JNJ-64565111 is available. The sponsor does not recommend specific intervention for an overdose, but rather appropriate symptomatic medical treatment should be given according to the clinical condition.

Decisions regarding dose interruptions or modifications will be made by the investigator in consultation with the Medical Monitor based on the clinical evaluation of the subject.

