On Day 1, subjects randomly assigned to the double-blind treatment arms will receive a supply of their randomly-assigned study drug and will be reminded of the once weekly dosing regimen and to record the date and time of each administered dose in the study drug diary. Subjects will self-administer the first dose of JNJ-64565111 or matching placebo at the site under the supervision of study staff.

Drug Administration

Subjects will be instructed to administer study drug SC once weekly for the entire duration of the 12-week treatment phase or until early discontinuation.

Subjects will be instructed to inject to the 4 quadrants of the anterior abdominal wall. For consistency, and to avoid dosing in the same abdominal area, subjects should be instructed to begin in one quadrant and on subsequent dosing days proceed in the next quadrant in a counterclockwise manner.

Injections can be done at any time of day irrespective of meals. However, it is preferable that study drug be injected during the same overall time period of the day on a week-to-week basis.

Study drug should be taken on the same day of the week throughout the study (ie, the regularly scheduled study drug day).

[figure not shown]
If the day of the once weekly injection coincides with the day of a clinic visit, subjects are NOT to inject JNJ-64565111 or matching placebo before arriving at the clinic. Instead, AFTER all study visit procedures have been completed, subjects may self-administer blinded study drug either at the study site or once they have returned home.

Subjects are to record the date and time of study drug administration on the study drug diary, and should mark a calendar to remind them of when to take the next weekly dose. Subjects will be instructed to record the date and time of each self-injection throughout the run-in and treatment phase which allows an assessment of treatment compliance and the relationship of PK measurements and safety assessments to the time of study-drug dosing. The information will be entered into eCRFs by the site personnel.

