Subjects should be instructed not to take 2 doses within 3 days (72 hours) of each other. If a subject misses taking the next dose of study drug on their regularly scheduled study drug day, the missed dose should be taken as soon as possible, if there are at least 3 days (72 hours) until their next regularly scheduled study drug day. If there are less than 3 days remaining, the subject should skip the missed dose and take the next dose on their regularly scheduled study drug day.

Study-site personnel will instruct subjects on how to store study drug for at-home use as indicated for this protocol. Figure 3 is a schematic diagram of the study drug injection schedule.

Figure 3: Schematic Diagram of Drug Injection Schedule

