An adverse event is considered unlisted if the nature or severity is not consistent with the applicable product reference safety information. For JNJ-64565111, the expectedness of an adverse event will be determined by whether or not it is listed in the Investigator's Brochure.

Adverse Event Associated With the Use of the Drug

An adverse event is considered associated with the use of the drug if the attribution is possible, probable, or very likely by the definitions listed below (see Attribution Definitions).

ATTRIBUTION DEFINITIONS**Not Related**

An adverse event that is not related to the use of the study drug.

Doubtful

An adverse event for which an alternative explanation is more likely, eg, concomitant treatment(s), concomitant disease(s), or the relationship in time suggests that a causal relationship is unlikely.

Possible

An adverse event that might be due to the use of the study drug. An alternative explanation, eg, concomitant treatment(s), concomitant disease(s), is inconclusive. The relationship in time is reasonable; therefore, the causal relationship cannot be excluded.

Probable

An adverse event that might be due to the use of the study drug. The relationship in time is suggestive (eg, confirmed by dechallenge). An alternative explanation is less likely, eg, concomitant treatment(s), concomitant disease(s).

Very Likely

An adverse event that is listed as a possible adverse reaction and cannot be reasonably explained by an alternative explanation, eg, concomitant treatment(s), concomitant disease(s). The relationship in time is very suggestive (eg, it is confirmed by dechallenge and rechallenge).

SEVERITY CRITERIA

An assessment of severity grade will be made using the following general categorical descriptors:

Mild: Awareness of symptoms that are easily tolerated, causing minimal discomfort and not interfering with everyday activities.

Moderate: Sufficient discomfort is present to cause interference with normal activity.

Severe: Extreme distress, causing significant impairment of functioning or incapacitation. Prevents normal everyday activities.

The investigator should use clinical judgment in assessing the severity of events not directly experienced by the subject (eg, laboratory abnormalities).

SPECIAL REPORTING SITUATIONS

Safety events of interest on a sponsor study drug in an interventional study that may require expedited reporting or safety evaluation include, but are not limited to:

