- Overdose of a sponsor study drug
- Suspected abuse/misuse of a sponsor study drug
- Accidental or occupational exposure to a sponsor study drug
- Medication error involving a sponsor product (with or without subject/patient exposure to the sponsor study drug, eg, name confusion)
- Exposure to a sponsor study drug from breastfeeding

Special reporting situations should be recorded in the eCRF. Any special reporting situation that meets the criteria of a serious adverse event should be recorded on the serious adverse event page of the eCRF.

PROCEDURES

All Adverse Events

All adverse events, regardless of seriousness, severity, or presumed relationship to study drug, must be recorded using medical terminology in the source document and the eCRF. Whenever possible, diagnoses should be given when signs and symptoms are due to a common etiology (eg, cough, runny nose, sneezing, sore throat, and head congestion should be reported as "upper respiratory infection"). Investigators must record in the eCRF their opinion concerning the relationship of the adverse event to study therapy. All measures required for adverse event management must be recorded in the source document and reported, according to sponsor instructions.

For all studies with an outpatient phase, including open-label studies, the subject should be provided with a "wallet (study) card" and instructed to carry this card with them for the duration of the study indicating the following:

- Study number
- Statement, in the local language(s), that the subject is participating in a clinical study
- Investigator's name and 24-hour contact telephone number
- Local sponsor's name and 24-hour contact telephone number (for medical staff only)
- Site number

- Subject number
- Any other information that is required to do an emergency breaking of the blind

Serious Adverse Events

All serious adverse events that have not resolved by the end of the study, or that have not resolved upon discontinuation of the subject's participation in the study, must be followed until any of the following occurs:

- The event resolves
- The event stabilizes
- The event returns to baseline, if a baseline value/status is available
- The event can be attributed to agents other than the study drug or to factors unrelated to study conduct

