10.2. Appendix 2: Regulatory, Ethical, and Study Oversight Considerations

REGULATORY AND ETHICAL CONSIDERATIONS

Investigator Responsibilities

The investigator is responsible for ensuring that the study is performed in accordance with the protocol, current ICH guidelines on Good Clinical Practice (GCP), and applicable regulatory and country-specific requirements.

Good Clinical Practice is an international ethical and scientific quality standard for designing, conducting, recording, and reporting studies that involve the participation of human subjects. Compliance with this standard provides public assurance that the rights, safety, and well-being of study subjects are protected, consistent with the principles that originated in the Declaration of Helsinki, and that the study data are credible.

Protocol Amendments

Neither the investigator nor the sponsor will modify this protocol without a formal amendment by the sponsor. All protocol amendments must be issued by the sponsor, and signed and dated by the investigator. Protocol amendments must not be implemented without prior IEC/IRB approval, or when the relevant competent authority has raised any grounds for non-acceptance, except when necessary to eliminate immediate hazards to the subjects, in which case the amendment must be promptly submitted to the IEC/IRB and relevant competent authority. Documentation of amendment approval by the investigator and IEC/IRB must be provided to the sponsor. When the change(s) involve only logistic or administrative aspects of the study, the IEC/IRB (where required) only needs to be notified.

During the course of the study, in situations where a departure from the protocol is unavoidable, the investigator or other physician in attendance will contact the appropriate sponsor representative listed in the Contact Information page(s), which will be provided as a separate document. Except in emergency situations, this contact should be made before implementing any departure from the protocol. In all cases, contact with the sponsor must be made as soon as possible to discuss the situation and agree on an appropriate course of action. The data recorded in the eCRF and source documents will reflect any departure from the protocol, and the source documents will describe this departure and the circumstances requiring it.

Regulatory Approval/Notification

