For summary statistics of serum JNJ-64565111 concentrations, concentration values below the lower limit of quantification will be treated as zero. Once a subject meets one of the following dosing deviation criteria, the subject's data will be excluded from the by-visit data analyses from that point onwards.

Dosing deviation criteria:

- Discontinued SC study agent administrations.
- Skipped a SC administration.
- Received an incomplete/ incorrect SC dose.
- Received an incorrect SC study agent.
- Received an additional SC dose.

In addition, if a subject has an administration more than 4 days earlier or later than the scheduled dosing date, the concentration data collected between such a dosing visit and the subsequent dosing visit will be excluded from the by-visit data analyses. For the Week 12 visit, if the PK sampling time deviates more than 4 days earlier or later than the scheduled date, the PK concentration at this visit will be excluded from the by-visit data analyses.

The conditions under which to exclude measurements from PK analysis:

- If date/time of Baseline sample is after date/time of first dose, then exclude the Baseline sample
- If Day 4 sample is  $>8$  days after 1st dose, then exclude the Day 4 sample
- If date of Week 2 sample – date of previous dose before date of Week 2 sample is  $< 3$  days or  $> 11$  days, then exclude Week 2 sample
- If date of Week 6 sample – date of previous dose before date of Week 6 sample is  $< 3$  days or  $> 11$  days, then exclude Week 6 sample

- If relative Study Day of Week 12 sample is < Day 80 or >Day 88 then exclude Week 12 sample
- If relative Study Day of Week 16 sample is < Day 108 or >Day 116 then exclude Week 16 sample
- If subject discontinues treatment early, then exclude the “Week 16” or “4 Week Follow-up” PK sample.

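### Does starting overdose at 4 injections in 7 days (Protocol 8.4) conflict with dosing rules that allow at most 2 (Protocol 6.1)?

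*Protocol*

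**What the plan says.** **Dosing instructions (Protocol 6.1, Drug Administration; repeated in the Synopsis).** The frequency is weekly: "Subjects will be instructed to administer study drug SC once weekly for the entire duration of the 12-week treatment phase or until early discontinuation". The dosing day is the same weekday throughout. Two further rules deal with lateness and spacing. For a late dose, "the missed dose should be taken as soon as possible, if there are at least 3 days (72 hours) until their next regularly scheduled" dosing day; with less time left, the dose is skipped. For spacing, "Subjects should be instructed not to take 2 doses within 3 days (72 hours) of each other".

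**Overdose (Protocol 8.4).** The definition is that "more than 3 doses/injections of JNJ-64565111 within a 7-day time period will be considered an overdose". When it is met, the Medical Monitor is contacted at once and the subject is followed closely for adverse events and laboratory abnormalities.

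**Other provisions that reach extra injections.**
- Protocol Appendix 1 (Special Reporting Situations) opens with "Safety events of interest on a sponsor study drug in an interventional study that may require expedited reporting or safety evaluation include". Its list includes overdose, misuse and medication error. It adds: "Special reporting situations should be recorded in the eCRF".
- Protocol Appendix 2, on departures from the protocol, says without exception that "contact with the sponsor must be made as soon as possible to discuss the situation and agree on an appropriate course of action".
- SAP 7.1 lists "Received an additional SC dose" among the dosing deviations that remove a subject's later data from the by-visit PK summaries.

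**The concern.** Read together, the two sections leave a band in between. A subject who injects three times in a week, or twice on the same day, has clearly broken 6.1 but has not had an overdose as 8.4 defines it. A site reading 8.4 literally would not have to make the immediate call or start the close monitoring.

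The 10 mg arm makes this look serious. Three injections there are 30 mg, twice the highest weekly dose given before (15 mg). Section 4.3 says doses above 10 mg were less well tolerated, Section 8.4 says there is no antidote, and most injections after Day 1 may be given at home. The SAP also plans for additional doses as an event that can occur. If the plan really left such events unhandled, subject safety would be at stake.

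**Working it through.** **1. What 6.1 allows.** Number the weekly slots k = 0, 1, 2, … A dose for slot k falls on day 7k + d. The delay d is 0 to 4, because at least 3 of the 7 days must remain.
- Two doses: 4 days late, then the next on schedule, is 7 − 4 = 3 days apart. Two doses in 7 days are compliant.
- Three doses: first to third is at least 14 − 4 = 10 days, which exceeds 7. Three are not compliant.
- The 72-hour rule alone: n doses need at least 3(n − 1) days. Three need 6 days and fit in 7; four need 9 and do not.

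So the full set of rules allows 2 in 7 days, and 8.4 starts at 4. Four is also the first count that cannot occur in 7 days without breaking the 72-hour spacing. The documents do not give this as the reason for the threshold; it is only an observation.

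**2. Is this a contradiction?** Section 6.1 is an instruction to the subject about when to inject. Section 8.4 is an instruction to the investigator about a response that becomes mandatory at a stated excess. No sequence of injections makes the two demand incompatible things. Nothing in 8.4 permits 3 injections, and nothing in it forbids contacting the Medical Monitor after 2 or 3. An overdose definition need not equal the dosing limit.

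**3. Do the protocol's own figures contradict the threshold?** Inputs are the Table 2 mean Cmax values (Section 2.2), in µg/mL: 5 mg, Week 1 0.259 and Week 4 0.565; 10 mg, 0.613 and 1.23. For 7.4 mg, linear interpolation at (7.4 − 5)/(10 − 5) = 0.48 gives 0.259 + 0.48 × 0.354 = 0.429 and 0.565 + 0.48 × 0.665 = 0.884.

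Assume linear superposition with coinciding peaks:

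mean peak = Week 4 Cmax + (injections − 1) × Week 1 Cmax

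| Same-day injections | 5 mg arm | 7.4 mg arm | 10 mg arm |
|---|---|---|---|
| 2 | 0.824 | 1.313 | 1.843 |
| 3 | 1.083 | 1.742 | 2.456 |
| 4 | 1.342 | 2.171 | 3.069 |

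The comparator is the 15 mg cohort at Week 4: mean 2.14, individual range 1.22 to 2.76.
- Two injections stay below 2.14 in every arm.
- Three pass 2.14 only in the 10 mg arm (2.456 / 2.14 = 1.15) and stay inside the range.
- Four in the 10 mg arm pass the highest individual peak (3.069 / 2.76 = 1.11). That is the count at which 8.4 begins.

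Section 2.2 says more than 90% of steady state was reached by Week 4. Scaling the 10 mg base accordingly gives 1.23 / 0.9 = 1.367. Two injections then give 1.980 and three give 2.593, still below 2.14 and 2.76 respectively.

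In injected amount, 3 × 10 = 30 mg is 30 / 15 = 2.0 times the highest earlier weekly dose. The first-in-human study also gave 4.0 nmol/kg as a single dose. Extrapolating Table 1 (5 mg per 1.0 nmol/kg for a 90 kg person), that is about 20 mg, so 30 mg is about 1.5 times the largest earlier single dose and two 10 mg injections equal it in amount.

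**4. What happens below the threshold.**
- Appendix 1: medication error or misuse is recorded in the eCRF and may require expedited reporting or safety evaluation.
- Appendix 2: sponsor contact as soon as possible on a departure from the protocol.
- Sections 6.1 and 6.4: every injection's date and time is recorded, supplies are reconciled, and non-compliant subjects are re-instructed.
- Section 8.2: subjects contact the site for severe nausea or vomiting, with clinical and laboratory assessment and possible interruption of study drug.
- Section 7.1: the investigator discontinues study drug for safety, or for persistently poor compliance.
- Section 8.3.1: adverse events are collected whether or not the event is called an overdose.

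**The case for a change.** The strongest case for the concern is that none of these routes prescribes the same two steps as 8.4. Appendix 1 requires an eCRF entry and says only that further evaluation may be needed. The Appendix 2 paragraph opens with departures that could not be avoided, so its fit to a self-injection mistake can be argued. Section 8.4 gives no basis for its threshold, which lies well above the 10 mg weekly dose that Section 4.3 treats as the upper end of the range.

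All of that is accurate, and the count of 2 against 4 is correct. The exposure comparison also has limits. It sets projected means against an individual range. Adding the highest individual 10 mg values in Table 2 gives 2.38 + 0.920 = 3.30 for two injections, above 2.76, although the two maxima need not belong to the same subject. Peaks are assumed to coincide, although Tmax ranged from 2 to 7 days after the first dose. The 12.4 mg cohort did not follow the pattern, and earlier repeat-dose PK was not dose-proportional. The projection is therefore neither a bound nor a validation of the threshold.

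None of this turns the difference into an inconsistency. What stands is a wish for 8.4's steps to begin earlier, which is a clinical judgement the documents do not decide. The SAP entry adds nothing, because it is a PK data-exclusion rule and says nothing about safety handling.

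**Conclusion.** The concern does not hold. Sections 6.1 and 8.4 serve different purposes and can both be followed. The events between them, 3 injections in 7 days or 2 that break the spacing or weekly rules, are outside 8.4 but not outside the plan's reporting, compliance and safety provisions. The protocol's exposure figures do not contradict the threshold: on projected means, the 10 mg arm first leaves the range seen in the 15 mg cohort at 4 injections.

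No effect on safety data, the efficacy analyses or the trial's conclusions is shown, and the documents give no frequency for extra dosing. The main conclusion rests on reading the passages side by side and would stand without the exposure projection, which depends on linear superposition, coinciding peaks and an interpolated 7.4 mg value. It is not a judgement that the threshold is clinically right. Any rationale in the Investigator's Brochure was not available for this review.
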